### Stopping Guidelines

**Stopping Early for Efficacy.** Improvements of physical activity are known to be difficult to maintain, so estimates of the durability of the effect, to be obtained at 1 year, will be important. In addition, the sedentary lifestyle this intervention addresses poses little risk of adverse events over the planned duration of the study. Accordingly, the slight delay in publishing results will be outweighed by the value of the information obtained from the longer term follow-up.

**Stopping Early for Futility:** To avoid wasting resources, it is important to allow for early stopping because the likelihood of finding convincing evidence for a treatment benefit appears too low, in the light of interim results, to justify continuation of the trial. Accordingly, futility analyses will be conducted at the time of each interim efficacy analysis. So-called stochastic curtailment procedures [Lan KKG, Simon R, Halperin M. Stochastically curtailed tests in long-term clinical trials. *Comm Statist, Series C (Sequential Analysis)*. 1982;1:207-219. Halperin M, Lan KKG, Ware JH, Johnson WJ, DeMets DL. An aid to data monitoring in long-term clinical trials. *Controlled Clin Trials*. 1982;3:311-323] will allow early stopping for futility if the conditional power to detect a beneficial effect is too low, given the data in hand. This lack of power should hold under plausible alternative hypotheses for the effect of treatment, including the effect assumed in determining the original sample size. Note that this procedure involves no inflation of the type-I error rate, in fact inducing slight conservatism. The DSMB would make the complex decision to stop early for futility in the light of the conditional power estimates, informed opinion about the plausibility of the alternatives considered, and other, broader considerations listed below.

**Stopping Early for Harm:** Because it would be unethical to require the same degree of certainty in repeated testing for a detrimental treatment effect as in repeated testing for benefit, protection of the type-I error rate becomes less important, and maintenance of power more pressing. Moreover, adverse effects on secondary endpoints must be considered, thus involving multiple endpoints as well as multiple looks. In view of these ethical and statistical complexities, stopping for harm will be done at the judgment of the DSMB, taking account of the seriousness and estimated excess risk of any observed adverse effects, the strength of the statistical evidence for them, and the broader guidelines listed below. In addition to considering each adverse event individually, the DSMB will consider all the data together, and any necessary additional analyses to be carried out by the data coordinating center, before making a recommendation that the trial be modified or stopped.

### **Reporting Temporary or Permanent Suspension of a Funded Clinical Trial**

The Principal Investigator will be responsible for immediately reporting to the National Institute of Aging (i.e., the Program Officer responsible for the grant), any temporary or permanent suspension of the project and the reason for the suspension.

## **9. STATISTICAL CONSIDERATIONS**

### **9.1 General Design Issues**

**Overview:** The primary analyses will be by treatment assignment, without regard to adherence to the intervention. Improvements in kyphosis, the Modified Physical Performance Test (PPT), and gait speed at 6 months will be co-primary endpoints. The Hochberg procedure will be used in testing the effect of treatment on these three endpoints. However, given fiscal and feasibility limitations on this

single-site study, tests of treatment effects on 5 additional physical function and HRQOL measures (Aim 2), as well as muscle strength and density (Aim 3), and all 9 comparisons at 1 year, will be regarded as secondary and analyzed without penalty for multiple comparisons, but with results clearly presented as hypothesis-generating.

In preliminary analysis, we will use t-, Wilcoxon, chi-square, and Fisher exact tests as appropriate to compare the treatment and control groups in terms of baseline age, gender, co-morbidities, vertebral fractures, physical activity and level of kyphosis. If between-group imbalances are found, sensitivity analyses will be conducted adjusting for the imbalanced covariates. However, the primary analysis will be unadjusted, to avoid inflation of type-I error and erosion of confidence due to model selection.

## 9.2 Sample Size and Randomization

**Sample size calculation:** We calculated minimal detectable effects (MDE) with 80% power in 2-sided tests with a Bonferroni-corrected type-I error rate of 5%, in a sample of 100, allowing for within-subject correlation of the baseline and 6-month outcomes, and loss to follow-up of 20% of participants. This trial is powered to detect a difference in change in kyphosis over 6 months of 2.2 degrees (or more) between the intervention and control groups. Although the expected improvement in kyphosis is small, the hypothesis underlying this study is that preventing the expected progression of kyphosis, and improving kyphosis even a small amount, in combination with improvements in strength and conditioning, will result in meaningful improvements in physical function. In addition, the MDE for PPT and gait speed are comparable to clinically meaningful changes defined by Perera. Moreover, the MDE for kyphosis, PPT and gait are plausible in view of our uncontrolled pilot study results showing mean improvement of 6 degrees in kyphosis, 2 points in PPT and 0.05 m/s in gait speed over 3 months. Even if regression to the mean and spontaneous improvement account for almost half of the mean improvement in our pilot study, our 6 month intervention is likely to yield benefits larger than the MDE in our trial. Standard methods for ANCOVA, positing reductions in residual variance by a factor of 1-r due to adjustment for the baseline value of the outcome, were used to obtain these estimates; here r is the within-subject correlation. We used data from the pilot study to estimate r as 0.8 for kyphosis and PPT, and 0.85 for gait speed; we also used pilot data to obtain residual SD (5, 2.6, and .18 respectively).

### 9.2.1 Treatment Assignment Procedures

**Randomization:** After the run-in period, participants will be randomized to the intervention group or control group. Participants will be randomized in equal proportions to intervention or control using randomly permuted blocks of randomly selected size 4 stratified by age and gender. Treatment assignments will be generated prior to the study, then placed in order in sealed, opaque

envelopes with stratum-specific sequential ID numbers. Consenting participants fulfilling study eligibility criteria will be assigned the next available ID number for the appropriate gender and age stratum. The date and time each envelope is opened will be recorded in a log along with participant ID to ensure integrity of randomization

***Additional Considerations in Interpreting the Data:*** In addition to the statistical procedures described above, other considerations will be taken into account in interpreting interim results. It is important for these additional considerations to be stated in advance to assure both study participants and investigators, who are masked to the data, that the DSMB will carefully consider many issues related to safety and efficacy and will recommend protocol changes or study termination if warranted. Two important additional considerations will be (1) the consistency of the observed

differences between treatment groups in variables that should be associated with one another, and (2) the importance of these differences to the health and the safety of individuals in the trial. Any differences between treatment groups in either outcome variables or adverse events will be considered for both their statistical significance and clinical importance. These considerations for interpretation of data require the combined expertise of clinical and statistical experts. A number of specific considerations for interpretation of these data can be stated in advance:

- Whether the magnitude or character of an observed difference constitutes a clinically important benefit or risk;
- Whether the risk under consideration is outweighed by assessment of the overall potential benefit of therapy;
- Whether the results could be explained by possible differences in baseline variables between the groups;
- Whether results could be due to ascertainment bias caused by differences in treatment regimens;
- Whether the results are consistent with those for other variables that should be associated with the variable in question;
- Whether the results are consistent among various subgroups of participants and across the various centers involved in the study;
- Whether it is likely that the current trends in the data could be reversed if the trial were to be continued unmodified;
- The degree of additional precision or certainty in the results that could be obtained by continuing the trial; and,
- Whether there would be significant loss in external validity or credibility of the trial by a change in Protocol or discontinuation.

In summary, a recommendation to modify or discontinue the trial would not be based solely on statistical grounds. Rather the DSMB supports the view voiced by Canner, on behalf of the Coronary Drug Project [Coronary Drug Project Research Group. Practical aspects of decision making in clinical trials: The Coronary Drug Project as a case study. *Controlled Clin Trials*. 1981;1(363-76)], that in clinical trial decision-making "No single statistical decision rule or procedure can take the place of the well reasoned consideration of all aspects of the data by a group of concerned, competent and experienced persons with a wide range of scientific backgrounds and points of view."

#### **9.4 Outcomes**

Baseline characteristics and outcome measures proposed in this study (Table 3) will be collected at baseline and after the 6-month intervention. All outcome measures except computed tomography will be repeated at 1-year after the intervention.

Table 3. Baseline Characteristics and Outcome Measures at Study Visits

Category	Variables: measure	Baseline Testing	6-month Testing	1-year Testing
Demographics - age, gender, ethnicity, education		X		
Aging-related musculoskeletal impairments				
- Bone density: hip BMD (DXA)	X			
- Vertebral fractures: lateral spine radiograph	X			
- Physical activity level: activity counts derived from Actigraph accelerometer	X	X	X	
Kyphosis-related impairments				
- Kyphosis: Cobb angle of kyphosis derived from lateral spine radiographs	X	X	X	
- Kyphosis: Kyphosis derived from Debrunner kyphometer	X	X	X	
- Spinal extensor muscle strength: Biomed computerized dynamometer	X	X	X	
- Spinal muscle density: spinal extensor muscle attenuation from CT scans (HU)	X	X		
Functional performance				
- Composite physical function: Modified Physical Performance Test	X	X	X	
- Gait speed: 4-meter	X	X	X	
- Mobility: Timed Up and Go test	X	X	X	
- Spine endurance: Timed Loaded Standing	X	X	X	
- Aerobic capacity/endurance: Six Minute Walk Test	X	X	X	
Health-Related Quality of Life				
- Spine-specific health-related quality of life: SRS-30	X	X	X	
- General health related quality of life: PROMIS Global Health	X	X	X	
- Physical function related quality of life: PROMIS Physical function short form	X	X	X	

#### 9.4.1 Primary outcome variables

Kyphosis: Kyphosis will be measured using the gold standard Cobb angle of kyphosis derived from standing lateral spine radiographs using a standardized protocol for thoracic kyphosis (T4-T12). The intraclass correlation coefficient (ICC) for repeated observer analysis of Cobb angle from the same radiograph is 0.99 and for single measurements taken from repeated radiographs is 0.82. When these estimates are combined, the ICC for radiographic measures of Cobb angle of kyphosis is 0.92, comparable to the ICC for kyphosis measurements using the Debrunner kyphometer 0.95.

The Modified Physical Performance Test (PPT): This battery was developed as a composite measure of overall physical function in the aging adult. The modified PPT includes 7-item timed standardized tasks: 50-foot floor walk, putting on and removing a lab coat, picking up and penny from the floor, standing up five times from a 16-inch chair, lifting a 7-pound book to a shelf, climbing one flight of stairs, and standing with feet together and two additional untimed tasks: climbing up and down

four flights of stairs and performing a 360° turn. The score for each item ranges between 0 and 4, with 36 representing a perfect total score for the test. Test-retest reliability for the modified PPT score in community-dwelling older adult population is 0.96. There is strong correlation with the Berg Balance Scale,  $r=0.7192$  and low scores on the modified PPT predict physical frailty.

Gait speed: A 4-meter walk test will be used to measure gait speed. Slow gait speed has been shown in several different populations to be the single best predictor of functional decline and disability. The object of the 4-meter walk test is to determine the individual's speed while walking at their usual and fast pace. Test-retest reliability is 0.90, ICC for measures taken 2-weeks apart is 0.79.

#### 9.4.2 Secondary outcome variables

Timed Up and Go test (TUG): TUG is a widely used clinical tool for detecting mobility impairments in older adults. This test measures the time to rise from a 48 cm height armchair, walk 3 m, turn and return to a fully seated position in the chair. This test has excellent reliability (ICC 0.91-0.96) and sensitivity and specificity for identifying elderly individuals at risk for mobility impairments and falls.

Timed Loading Standing: Timed Loading Standing is a test of combined trunk and arm endurance that measures the time a person can stand while standing a two-pound dumbbell in each hand with the arms at 90 degrees of shoulder flexion and the elbows extended. The ICC for same day inter-trial and 6 to 10-day test retest reliability is 0.89. Moderately high correlations were found between Timed Loaded Standing and 16 measures of physical impairment and function.

Spinal extension muscle strength: We will use a standardized protocol for spine muscle extensor muscle strength using the Biodex (Biodex Medical Systems Inc.) computerized dynamometer with the spine attachment to measures isometric peak torque to body weight ratio of spinal extension from semi-seated position. The ICC for 1-week test retest reliability is 0.84 (95% CI=0.71, 0.96).

Spinal muscle density: Muscle density of the lumbar paraspinal muscles will be determined from calculations of fat infiltration into the paraspinal muscles at the L4-L5 disc space from axial computed tomography (CT) images using proprietary software (RSI Systems, Boulder, CO). Measurement of fat infiltration from CT images has been validated in muscle biopsy studies. The coefficient of variation for reproducibility of spinal muscle density values among older adults is less than 5%. [name] developed the software, he will train our study staff to use the software and oversee quality control of the measurements.

Six-minute Walk Test (SMWT): The SMWT is a widely used test of aerobic capacity; there are gender specific normative data available for community-dwelling older adults. One week test retest reliability is 0.95 and compares with cycle ergometry  $r=0.58$ .

#### Additional outcomes

Health related quality of life (HRQOL): We will use the modified Scoliosis Research Society SRS-30 instrument, (self-image domain only), and the PROMIS Physical Function and Global Health questionnaires. The pain and general self-image domain scores of the SRS-30 have significant correlation with Cobb angle of kyphosis in untreated scoliosis. Internal consistency, Cronbach's alpha, was 0.77 to 0.89 for all domains; validity of the modified SRS-30, determined by Pearson correlation coefficients with comparable SF-36 domains, was 0.70 for 13 of 14 relevant domains.

Other study measures: We will measure height and weight using standard methods, and collect a history of falls and current medications from detailed questionnaires. Bone density of the spine and hip will be measured using Dual X-ray Absorptiometry (DXA) and vertebral fractures will be adjudicated from T4 to L4 with lateral spine radiographs at baseline. Participants will complete a numeric rating pain scale, and adverse event log before participating in each exercise class. Physical activity will be measured with actigraphy.

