**Hyperkyphosis is not synonymous with spinal osteoporosis.** It is often assumed that hyperkyphosis is caused solely by osteoporosis and vertebral fractures, but only a third of individuals with severe hyperkyphosis have radiographic vertebral fractures. In fact, recent evidence suggests that impairments in spinal muscle composition, strength, mobility and alignment are important determinants of the degree of kyphosis. Higher multisegmental spinal loads and trunk muscle forces are present in the hyperkyphotic vs. normal spine, and improving the biomechanics of spinal load and muscle force distribution could potentially ameliorate the detrimental effects of kyphosis and slow kyphosis progression. To date, small studies have demonstrated that kyphosis-related impairments can be targeted with exercise, but none have established whether reducing these impairments prevents kyphosis progression, or leads to improvement in physical function.

- ***Spinal muscle weakness.*** Spinal extensor muscle strength is an important independent determinant of degree of kyphosis in older adults. Recent studies demonstrate that spinal extensor muscle strength can be increased with targeted strengthening, however the effects on kyphosis have been inconsistent. The only large randomized exercise trial did not improve Cobb angle or Debrunner kyphometer kyphosis. High-intensity strengthening rather than low-intensity or yoga-type exercise may be necessary to reduce the Cobb angle or Debrunner kyphosis.
- ***Spinal muscle fat infiltration.*** We examined fat infiltration in the spinal extensor

muscles on quantitative computed tomography (CT) among healthy community-dwelling older men and women and found lower spinal muscle density (a proxy measure of fat infiltration) among older adults with hyperkyphosis. Furthermore, lower spinal muscle density is a known predictor of impaired physical function in older adults, suggesting that improved muscle quality is a possible mechanism for improving physical function that we will investigate in our study.

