Participants will come in to the UCSF Clinical Research Center study site for kyphosis-related impairment, functional performance and health related quality of life measurements. They will receive spinal radiographs and computed tomography scans at the UCSF Department of Radiology.

**Intervention/Control Study Visits:** Participants assigned to the intervention group will receive a kyphosis-specific spinal strengthening group exercise program for 1 hour three times per week for 6 months, followed by 6 months of usual activity. The participants assigned to the control group will receive a non-specific stretching group program for 1 hour three times per week for 6 months, followed by 6 months of usual activity. The intervention and the control group sessions will be conducted at one of the intervention study sites, including the UCSF PhysFit Physical Therapy Health and Wellness Center at the Mission Bay campus, Kaiser Permanente French campus (pending), VA Medical Center (pending) and the Osher Center for Integrative Medicine (pending). A licensed physical therapist will teach the kyphosis-specific strengthening exercise intervention and a different physical therapist will teach the stretching intervention. Physical therapy students and/or research assistants will help ensure the safety of all participants and maintain a ratio of no more than 5 participants to 1 teacher.

**Test Visit 2 (6 month):** Participants will come in to the UCSF Clinical Research Center study site for kyphosis-related impairment, functional performance and health related quality of life measurements. They will receive spinal radiographs and computed tomography scans at the UCSF Department of Radiology.

**Maintenance Period:** At the end of 6 months, participants will continue usual activity during the maintenance period. Participants will receive phone calls to wear the step-counter for a week each month to monitor physical activity during the maintenance period.

**Test Visit 3 (1 year):** At the end of one year, participants will be re-measured at the UCSF Clinical Research Center study site for kyphosis-related impairment, functional performance and health related quality of life measurements. They will receive spinal radiographs only at the UCSF Department of Radiology.

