## 7.6 Safety Monitoring

The DSMB will make decisions based on pre-specified guidelines detailed below. Decision-making will explicitly include consideration of both statistical and non-statistical issues.

Subjects will have an opportunity to privately discuss any musculoskeletal or other physical complaints due to study exercise with a member of the research study staff on a weekly basis at the beginning of an exercise session. Participants will also have a contact number to report any potential adverse events that occur in between scheduled study visits. We will monitor participants during the study visits, and teach participants to self-monitor during study visits to prevent injury during the testing or exercise sessions. All participants will complete an adverse event log, including pain scale, falls and any injuries before each study visit. [name] will be responsible for monitoring the study for patient safety and adverse events, and reviewing these logs on a daily basis. The DSMB will meet twice a year to review study progress and adverse events.

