## **15. SUPPLEMENTS/APPENDICES**

### **I. PROCEDURES SCHEDULE**

Assessment	Phone Screen	Clinic Screen	Medical Screen	Run In	Test Visit 1 (Baseline)	Intervention/Control Visits (1-72)	Test Visit 2 (6 month)	Maintenance Period	Test Visit 3 (1year)
Informed Consent Form		X							
Group Orientation (explain study)		X		X					
Basic Demographics	X				X				
DXA					X				
Lateral Spine Radiograph					X		X		X
Medical History	X		X						
Screen (gait, kyphosis, safety assessment)		X							
Current Medications	X		X						
Contact primary care providers for OK			X						
Inclusion/Exclusion Criteria	X	X	X						
Enroll		X							
Randomize					X				
Intervention/Control Study Visit						X			
Kyphosis: Cobb angle of kyphosis					X		X		X
Kyphosis: Debrunner					X		X		X
Spinal muscle strength: Biodex computerized dynamometer					X		X		X

Assessment	Phone Screen	Clinic Screen	Medical Screen	Run In	Test Visit 1 (Baseline)	Intervention/Control Visits (1-72)	Test Visit 2 (6 month)	Maintenance Period	Test Visit 3 (1year)
Spinal muscle density: CT scans					X		X		
Functional Performance					X		X		X
Health-Related Quality of Life					X		X		X

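### Vertebral fractures are read on the baseline film only, although the same film is repeated twice, so new fractures that participants do not notice never reach the DSMB

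*Combined protocol and SAP*

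**What the plan says.** **Fracture reading.** Section 9.4.2, under Additional outcomes, states that "vertebral fractures will be adjudicated from T4 to L4 with lateral spine radiographs at baseline". Table 3 in section 9.4 agrees: the row "Vertebral fractures: lateral spine radiograph" carries one mark, while the row "Cobb angle of kyphosis derived from lateral spine radiographs" carries three (baseline, 6 months, 1 year).

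**Films.** The procedures schedule in Appendix I marks "Lateral Spine Radiograph" at all three test visits. Section 6.2 says of the 6-month visit, "They will receive spinal radiographs and computed tomography scans at the UCSF Department of Radiology", and of the 1-year visit, "They will receive spinal radiographs only at the UCSF Department of Radiology".

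**Use of fractures.** Section 9.1 compares them between groups at baseline. Section 9.5 lists them among the confounders in the Aim 3 model. No section defines a new-fracture variable or a new-fracture safety outcome.

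**Safety capture.** Section 7.6 says, "All participants will complete an adverse event log, including pain scale, falls and any injuries before each study visit". It also gives participants a weekly private talk with staff at the start of a session and a contact number for events between visits. The DSMB meets twice a year (sections 7.2 and 7.6).

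**The concern.** The active arm progresses to high-intensity resisted spinal extension in people aged 60 or older with hyperkyphosis. Section 2.1 reports that "only a third of individuals with severe hyperkyphosis have radiographic vertebral fractures". Section 4 excludes only painful vertebral fractures of the past 6 months, so people with painless or older fractures can enrol. A new vertebral fracture is thus a structural harm that this trial should be able to report.

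Under Stopping Early for Harm in section 8, the DSMB is to weigh the seriousness and estimated excess risk of observed adverse effects. A fracture that causes no recognised symptom, on a film that nobody reads for fracture, is never observed. The trial could then report no vertebral fractures without having looked for them, although the films would be on file.

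**Working it through.** **1. What is taken and what is read** (section 6.2, Table 3, Appendix I)

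| Visit | Lateral film taken | Cobb angle derived | Fractures adjudicated |
|---|---|---|---|
| Baseline | yes | yes | yes |
| 6 months | yes | yes | no |
| 1 year | yes | yes | no |

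The Cobb angle is measured from T4 to T12 (section 9.4.1), which lies inside the T4-L4 range read at baseline.

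**2. Whether another route closes the gap**

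- Class log (Weekly Log form in Appendix III): asks about falls and injuries since the last class, with a fracture tick box. It depends on a noticed injury. Section 9.4.2 ties it to exercise classes; section 7.6 ties it to study visits. Even if it were also completed at the 1-year visit, it would still depend on a noticed injury.
- Weekly talk with staff (section 7.6): held at the start of an exercise session, so it ends with the classes.
- Contact number (section 7.6) and adverse event form (Appendix III): not limited to the class period, but they need a noticed event.
- Maintenance period (sections 5.1 and 6.2): the planned contact is a call about wearing the activity monitor.

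None of these detects a fracture that the participant does not notice.

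**3. What reading the films would give**

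The plan states no fracture rate or precision target, so there is no figure to reproduce. Inputs from section 9.2: 100 participants and 20% loss. With 1:1 allocation, that is 50 per arm, or 50 x 0.80 = 40 with loss.

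If no new fracture is seen among n participants in an arm, the exact one-sided 95% upper limit is 1 - 0.05^(1/n):

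- n = 50: 1 - 0.05^(1/50) = 0.058, or 5.8%
- n = 40: 1 - 0.05^(1/40) = 0.072, or 7.2%

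Without the reads, no such limit can be given for silent fractures.

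The chance of seeing at least one case in an arm is 1 - (1 - p)^n. The rate p is an assumption, taken here as 1% to 5%:

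- n = 50: 0.395 to 0.923
- n = 40: 0.331 to 0.871

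**4. What reading the films would not give**

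Two-sided Fisher exact test with every case in one arm of 50:

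- 5 v 0: 2 x C(50,5)/C(100,5) = 2 x 2,118,760/75,287,520 = 0.056
- 3 v 0: 2 x C(50,3)/C(100,3) = 2 x 19,600/161,700 = 0.24

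A formal comparison between arms would settle little. The value lies in finding cases and putting limits on the rate in each arm.

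**5. Number of films**

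2 visits x 100 = 200 at most; 200 x 0.80 = 160 with 20% loss.

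**The case against.** A reader might infer that unread fractures compromise the co-primary Cobb endpoint. The documents do not support that. The primary analysis is by assignment (section 9.1). If the exercise causes fractures that raise the Cobb angle, the rise belongs to the treatment effect and is already in the follow-up measurement. Fractures equally frequent in both arms leave the expected contrast unchanged. Reading the films could explain a Cobb result but would not correct it. Nor can a size be put on it, since the documents give neither a rate of new fractures nor degrees of Cobb angle per fracture.

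A reader might also infer that fractures go unrecorded altogether, or that they will be common. Neither follows. Noticed fractures have several routes into the safety data. The one-third figure in section 2.1 is a prevalence in severe hyperkyphosis, cited there to argue that kyphosis is not simply a product of fracture. Section 4 also removes some people at higher risk (prolonged oral glucocorticoids, three or more falls, recent hip fracture). Section 2.3 reports no serious exercise-related events in a review of 121 trials, although section 2.2 and what follows it concede that those trials did not focus on hyperkyphosis.

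Finally, the films will exist and could be read after the trial. That stands, but a late read would not serve the DSMB's twice-yearly reviews. The radiology department may issue routine reports; the documents do not say so, and they describe no route from such reports to the DSMB.

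**Conclusion.** The point holds as a gap in safety ascertainment. The plan sets a baseline-only rule, and following it leaves silent new vertebral fractures unobserved in both arms for the whole year. It is a cheap improvement, not a flaw in the primary analysis.

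Its size is what the DSMB cannot say: with zero events in an arm, an upper limit of about 5.8% (n = 50) or 7.2% (n = 40). Those limits rest on films being read for every participant counted. They also assume that the follow-up films show the same levels as the baseline film. The documents give all three films the same name but do not state the field of view; if a follow-up film covers less than T4-L4, the limits apply only to the levels seen.

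**What to change.** In section 9.4.2 and Table 3, extend the T4-L4 adjudication to the 6-month and 1-year films. Have them read blinded to arm and against the baseline film, by whoever does the baseline adjudication (the documents name no reader). Confirm that the follow-up films cover those levels. Read them as they accrue, so that the results reach the scheduled DSMB meetings. Report new fractures by arm to the DSMB as a descriptive safety outcome with confidence limits and no formal test.

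Leave the by-assignment Cobb analysis unchanged. Do not add an analysis that excludes participants with a new fracture: it would condition on a post-randomisation event that the exercise may have caused, and if so would favour the exercise arm. At most, list those participants' Cobb changes descriptively.

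The cost is reading time on up to 200 existing films (about 160 with 20% loss) and a route for passing incidental findings to the study physician. No visit, film, radiation or sample size is added.
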